6.8 Safety Assessments

There will be no planned safety assessments as the risks for the participants are considered minimal (see section 1.3).

6.9 Other Study Procedures

No other study procedures are planned.

7 Safety and Incident Reporting

Given that this is a quantitative accuracy study of clinical biochemistry point-of-care assays, the probability of an adverse event (AE) or a serious adverse event (SAE) occurring to a study participant to be associated with the investigational products is extremely low (see Appendix 1 for definitions of AE or SAE). Considering this, only deaths occurring between the start of the fingerstick blood collection and until the participant leaves the study will be recorded on a standardized form and reported to FIND by the investigator within 24 hours of becoming aware.

7.1 Medical Device Incidents (including Malfunctions)

Medical devices are being provided for use in this study for the purpose of assessing their diagnostic accuracies. In order to fulfil regulatory reporting obligations worldwide, the investigator is responsible for the detection and documentation of events meeting the definitions of incident or malfunction that occur during the study with such devices.

The definition of a Medical Device Incident can be found in Appendix 2.

Examples of a medical device incident for this study could be:

- A broken sample collection device (if provided)
- A broken or malfunctioning capillary tube or pipette provided

NOTE: Incidents fulfilling the definition of an SAE will also follow the processes outlined above and in Appendix 2 of the protocol.

7.2 Time Period for Detecting Medical Device Incidents

Medical device incidents or malfunctions of the device that result in an incident will be detected, documented, and reported during all periods of the study in which the medical device is used.

If the investigator learns of any incident at any time after a participant has been discharged from the study, and such incident is considered reasonably related to a medical device provided for the study, the investigator will promptly notify FIND.

The method of documenting Medical Device Incidents is provided in Appendix 2.

7.3 Follow-up of Medical Device Incidents

All medical device incidents involving an SAE will be followed and reported in the same manner as other SAEs (see Section 7.1.2). This applies to all participants, including those who discontinue study intervention.

The investigator is responsible for ensuring that follow-up includes any supplemental investigations as indicated to elucidate the nature and/or causality of the incident.

New or updated information will be recorded on the originally completed form with all changes signed and dated by the investigator.

7.4 Reporting of Medical Device Incidents to FIND

Medical device incidents will be reported to FIND within 24 hours after the investigator determines that the event meets the protocol definition of a medical device incident.

The Medical Device Incident Report Form will be sent to FIND by email. If email is unavailable, then a mobile phone photo and text messaging should be utilised.

The same individual(s) will be the contact for the receipt of medical device incident reports and SAE reports.

7.5 Regulatory Reporting Requirements for Medical Device Incidents

The investigator will promptly report all incidents occurring with any medical device provided for use in the Study in order for FIND to fulfil the legal responsibility to notify appropriate regulatory authorities and other entities about certain safety information relating to medical devices being used in clinical studies.

The investigator, or responsible person according to local requirements (e.g., the head of the medical institution), will comply with the applicable local regulatory requirements relating to the reporting of incidents to the IRB/IEC.

8 Statistical Considerations

This section provides summary of the planned statistical analyses of the primary and secondary endpoints, as well as details on the sample size calculation. A Statistical Analysis Plan (SAP) will be written before the start of recruitment and will describe the analysis strategy in detail. Analysis of the exploratory objectives will be described in the SAP.

8.1 Populations for Analyses

For purposes of analysis, the following populations will be defined as per Table 3.

TABLE 3: POPULATION FOR ANALYSIS

Population	Description
Enrolled	All participants who sign the informed consent
Evaluable/Per Protocol Population (PP)	All participants who fully complied with the protocol and for whom index test results and reference test results are available for all tests.
Partially Compliant Population (PCP)	All participants who complied partially with the protocol, i.e. those for whom index test results and reference test results are available but not in a complete form (e.g. missing one POC result)

8.2 Statistical Analyses

8.2.1 Analysis of primary and secondary outcomes

The primary and secondary outcomes of the study are presented in the Table 4.

TABLE 4: ENDPOINTS AND ANALYSIS METHOD

Endpoints	Analysis method
Primary	
1.1 Estimates of correlation and linear dependence between quantitative measurements of glucose, HbA1c, total cholesterol and creatinine evaluated in a healthcare setting with point-of-care multiparameter devices and in a laboratory reference assay.	1.1 Point estimates of Pearson correlation coefficient, coefficient of determination (R^2), intercept and slope coefficient of linear regression (with 95% confidence intervals), will be computed for all biomarkers and devices compared to the reference assay.
1.2 Estimates of accuracy and limits of agreement for quantitative measurements of glucose, HbA1c, total cholesterol and creatinine evaluated in a healthcare setting with point-of-care multiparameter devices (compared to a laboratory reference assay).	1.2 Point estimates of fixed and proportional bias (with 95% confidence interval), coefficient of variation and limits of agreement, calculated via Bland-Altman analysis in absolute and relative units, will be computed for all biomarkers and devices compared to the reference assay.
Secondary	

2.1 Operational characteristics and usability of study devices:
 
 - Rate of invalid test results and error types - System usability score 	
2.1 Proportion of invalid tests per parameter (with 95% confidence interval based on Wilson's score method) will be computed for each device. System usability score will be analyzed with descriptive statistics.

---	---

Point estimates of correlation between concentrations of biomarkers, measured with the POC devices and reference assay, will be calculated based on Pearson's method separately for each device and marker type. The dependence between the measurements of POC devices and the reference method will be visualized with the use of scatter plots and analyzed using linear regression. Point estimates of intercept and slope coefficient, with 95% confidence intervals, and coefficient of determination (R^2) will be computed separately for each device and marker type.

To evaluate the systemic deviation of POC device measurements from the established reference assay, Bland-Altman analysis will be performed for each marker type and device. The deviation will be visualized with the Bland-Altman plot in absolute and relative units. Point estimates of fixed bias (mean difference between measurements) and proportional bias (dependence of the difference on concentration level), with 95% confidence intervals, will be computed. Standard deviation of the difference between the measurements of POC device and reference assay will be evaluated, along with the coefficient of variation and 95% prediction interval (limits of agreement) of the error. All calculations will be performed in absolute and relative units.

Secondary endpoints include the evaluation of system usability score and proportion of invalid tests for POC devices. The mean and 95% confidence interval will be estimated for these characteristics separately for each device. Confidence interval for the proportion of invalid tests will be calculated based on Wilson's score method.

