6.3.2 Reference tests

Reference testing will be done at the B.P. Koirala Institute of Health Sciences. The reference test for HbA1c will be the HbA1c Immunoassay (A1C) on the Roche cobas analyzer, which requires 3 ml of whole blood using K2-EDTA as anticoagulant. This is a validated sample type for this analyzer as per the manufacturer's instruction for use.

The reference tests for glucose, for total cholesterol and creatinine will be based on Enzymatic test principles, on the Roche cobas analyzer. Creatinine (CRE) and total Cholesterol (CHOL) are requiring 4 ml of whole blood (for 2ml of Serum) for analysis in total, and Glucose (GLU) 2 ml of whole blood (1.5 ml of Plasma). All sample types are validated by the manufacturers for use with the respective tests.

All reference tests will be performed according to the manufacturer's instruction for use and quality controls and calibrations for the tests are performed by the laboratory according to the manufacturers' recommendations (or based on the laboratories standard operating procedures for quality assurance of tests).

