8.4 Sample Size Determination

Available data from an external evaluation study of the performance of the Tascom and Jana Care assays, showed Pearson correlation coefficients greater than 0.98 for all markers compared to the reference laboratory standard [xxx = reference corresponding to Excel table]. The precision estimated as the standard deviation of difference of measurements compared to reference divided by the mean concentration (%CV) was in range of 1.8-4.1% for SimplexTas 101 and 1.9-3.9% for Jana Care, depending on the marker and its concentration.

TABLE 5: INVESTIGATIONAL PRODUCTS PERFORMANCE CLAIMS AS PER IFU

Assay	ρ , Pearson correlation	Precision (%CV) at low and high concentrations
SimplexTAS 101 Glucose	0.998	Low = 2.5% High = 1.8%
SimplexTAS 101 HbA1c	0.995	Low = 3.6% High = 2.4%
SimplexTAS 101 Total cholesterol	0.996	Low = 4.1% High = 2.5%
SimplexTAS 101 Creatinine	0.997	Low = 4.1% High = 2.4%
Jana Care Glucose	0.995	Low = 2.7% High = 2.4%
Jana Care HbA1C	0.99	Low = 1.9% High = 2.5%
Jana Care cholesterol	0.981	Low = 3.9% High = 3.7%

Considering the possibility of a lower performance of POC device outside of the manufacturer's laboratories, the Pearson's correlation coefficient and precision were conservatively assumed to be 0.9 and 5%, respectively. Based on this assumption, at least 337 samples (for each marker and device) will be needed to detect statistically significant $\pm 1.5\%$ fixed bias of POC measurements compared to the reference (using two-tailed t-test with 80% power and 5% significance level).

To improve the precision of the test, the number of samples per marker analyzed in this study was increased to 400 per device, recruited at two trial sites. Assuming that the expected Pearson's correlation coefficient (ρ) between POC and reference measurements is 90%, 95% or 99%, the proposed sample size will allow to estimate ρ with the 95% confidence interval of 88–91.7%, 93.9–95.9% and 98.8–99.2%, respectively.

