10.2 Data Management

Data Management procedures at FIND, including the setup of the database, programming edit and range checks and querying, are described in the Data Management Plan.

Site staff will be responsible for entering their data from a paper CRF into OpenClinica. Detailed timelines for data transfer will be provided in the Study Manual. Data will be cleaned of errors by FIND throughout the study as it is captured electronically.

The investigator is responsible for verifying that data entries are accurate and correct. Data entered in the OpenClinica database must be consistent with the source documents or the discrepancies must be explained.

The site will be provided with individual password-protected accounts to access OpenClinica, following a training session given by FIND.

OpenClinica provides an audit trail system recording all data entries/changes and queries between FIND and the site. Data entry training will be provided by FIND, either on site or remotely sharing screen through Skype or any other similar system.

No information concerning the study or the data generated from the study will be released to any unauthorized third party without prior written approval of FIND.

11 Quality Management

Quality Management for this study consists of Quality Control activities, training and capacity building provided by FIND (or designee) to the investigational sites, as well as the use of Standard Operating Procedures, Work Instructions, Tools and Templates. Prior to study start FIND will verify that the reference laboratory has adequate quality management procedures in place to ensure

reliability of test results. This will be verified by reviewing relevant quality management system (QMS) documents of the laboratory and verifying evidence of adherence through e.g. availability of analyser calibration and control results.

Training on the protocol, GCP and the use of the POC tests will be provided by FIND. A study Manual, which describes all of the sample testing procedures, will be provided by FIND prior to the commencement of the study. Training on the EDC system will be provided by FIND Data Management prior to first participant enrolment.

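### Endpoint 1.1 takes slope and intercept from ordinary regression on an error-prone laboratory value, so an unbiased device is expected to show a slope below 1 and an intercept above 0, mainly for HbA1c

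*Protocol*

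**What the plan says.** Table 4, row 1.1, makes correlation and linear dependence a primary endpoint and lists "intercept and slope coefficient of linear regression (with 95% confidence intervals), will be computed for all biomarkers and devices compared to the reference assay". The text of section 8.2.1 repeats the method: the relation "will be visualized with the use of scatter plots and analyzed using linear regression", and "Point estimates of intercept and slope coefficient, with 95% confidence intervals, and coefficient of determination (R^2) will be computed separately for each device and marker". No errors-in-variables method, such as Deming or Passing-Bablok, is named anywhere in the protocol.

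The comparator is a laboratory analyser. Section 6.3.2 states "The reference tests for glucose, for total cholesterol and creatinine will be based on Enzymatic test principles, on the Roche cobas analyzer", and HbA1c is an immunoassay on the same platform. The protocol gives no imprecision for the reference assays and describes no replicate reference testing. Section 8.4 plans on figures in which "the Pearson's correlation coefficient and precision were conservatively assumed to be 0.9 and 5%, respectively". It defines precision through the differences: "The precision estimated as the standard deviation of difference of measurements compared to reference divided by the mean concentration (%CV"). The planned number is fixed where "the number of samples per marker analyzed in this study was increased to 400 per device".

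Endpoint 1.2 separately estimates fixed bias (the mean difference) and proportional bias (how the difference depends on concentration) by Bland-Altman analysis.

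**The concern.** Ordinary regression assumes that x is measured without error. Here x is a single venous result with its own analytical error, obtained after centrifugation, cold storage and transport. Independent error in x shrinks the expected slope by the ratio of true variance to true plus reference-error variance, and the lost part reappears as a positive intercept. This is bias in the point estimate. More participants or robust standard errors do not remove it.

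Table 2 presents the manufacturers' slopes and intercepts as device performance, for example 0.973 for Jana Care HbA1c and 0.949 for Jana Care cholesterol. Readers are likely to set this study's slopes beside them. Laboratory error would then count against the device, most where the concentration range is narrow.

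**Working it through.** **The plan's own figure.** Fisher's z intervals, tanh(atanh(ρ) ± 1.96/√397), give 0.880–0.917, 0.939–0.959 and 0.988–0.992 for ρ = 0.90, 0.95 and 0.99. These match section 8.4.

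**Formula.** For a device with no bias, with B = between-person SD/mean and R = reference CV (both in % of the mean):

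- expected slope = B²/(B² + R²)
- expected intercept = (1 − slope) × mean

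**Assumed spreads.** Neither B nor R is in the protocol, so both are assumptions.

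| B | R = 1% | R = 2% | R = 3% |
|---|---|---|---|
| 11% | 121/122 = 0.992 | 121/125 = 0.968 | 121/130 = 0.931 |
| 17% | 289/290 = 0.997 | 289/293 = 0.986 | 289/298 = 0.970 |
| 21% | 441/442 = 0.998 | 441/445 = 0.991 | 441/450 = 0.980 |

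The first two rows stand for HbA1c and the third for cholesterol. The intercept is the complement: at B = 11% and R = 2–3% it is 3.2–6.9% of the mean. Simulation with n = 400, constant-CV errors, POC CV 4% and no device bias agrees: 0.967 and 0.930 at B = 11%, and 0.986 and 0.969 at B = 17%, for R = 2% and 3%. For long-tailed glucose and creatinine the loss is 1% or less.

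**From the planning values.** Take ρ = 0.9 and an SD of the difference of 5% (variance 25), with no device bias. If the reference has no error, B²/(B² + 25) = 0.81, so B = 10.3%. If error is shared equally, B²/(B² + 12.5) = 0.9, so B = 10.6%. A spread near 11% is therefore what the planning values imply. Solving in between:

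| R | Slope | Intercept, % of mean |
|---|---|---|
| 1% | 0.991 | 0.9 |
| 2% | 0.965 | 3.5 |
| 3% | 0.926 | 7.4 |
| 3.5% (equal share) | 0.900 | 10.0 |

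**From the claimed correlations.** Table 5 gives ρ of 0.981–0.998. With equal error shares the expected slope equals ρ, so it is 0.981–0.998 overall and 0.990–0.995 for HbA1c.

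**Endpoint 1.2.** The mean difference does not involve x-error attenuation. Proportional bias depends on the axis, which section 8.2.1 does not name. Regressed on the reference at B = 11%, R = 2%, it is 0.968 − 1 = −3.2%. Regressed on the mean of the two methods with POC CV 4%, it is [(16 − 4)/2]/[121 + (16 + 4)/4] = 6/126 = +4.8%. Both are for a device with no bias.

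**Does Deming regression repair it?** With the correct error ratio, the mean slope in simulation was 1.00 in every scenario. The source of the ratio matters. Suppose the true POC CV is 5%, the assumed one 2.5%, R = 2% and B = 11%. With constant-CV errors the variances are 121 + 4 × 1.0121 = 125.05 (reference) and 121 + 25 × 1.0121 = 146.30 (POC), the covariance is 121, and the assumed ratio is λ = (2.5/2)² = 1.5625. The slope is [146.30 − 195.39 + √(49.09² + 4 × 1.5625 × 121²)]/242 = 1.06. At R = 1.5% the same steps give 1.04. Ordinary regression gives 0.97 and 0.98, so a ratio built on an optimistic POC CV does worse than no correction. A correction using only the reference error returned 1.00.

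**The case against.** **Estimand.** Endpoint 1.1 is worded as linear dependence between two measurements, and ordinary regression does estimate how the POC reading depends on the laboratory reading. Bias in the device is assigned to endpoint 1.2. This stands in part: the mean difference there is sound, so the overall bias estimate is not compromised. It does not rescue the slope and intercept, which are reported for a study of accuracy, and the proportional bias in 1.2 is open to the same attenuation.

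**Size.** The reference CV and the spread are both assumed, and the effect is small if the analyser is precise or the range wide. This stands. A reader might infer from ρ = 0.9 that slopes near 0.90 are to be expected. The documents do not support that: the value is a deliberately cautious planning figure, and 0.90 also requires the laboratory to be as noisy as the device.

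**Decisions.** A reader might also infer that devices would be wrongly declared biased because the interval excludes 1. The protocol plans no test of slope = 1 and sets no acceptance limit for slope or intercept, so there is no such decision error.

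**Deferral.** Section 8 calls itself a summary, and the SAP is not shown. The word ordinary does not appear, and the SAP could name another fit. But unqualified linear regression with R^2 is stated twice as the primary method, and its normal reading is least squares.

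**Conclusion.** The point holds in a limited form. As written, endpoint 1.1 gives a slope that is expected to be too low and an intercept that is too high for an unbiased device. Under assumed SD/mean of 11–17% and reference CV of 1–3%, the slope lies between about 0.997 and 0.93. The effect is material mainly for HbA1c, smaller for cholesterol, and under 1% at a reference CV of 1%. At the upper end it is as large as the departures from 1 in the manufacturers' own equations. The result assumes that reference and POC errors are independent and that the planned fit is ordinary least squares. It does not extend to the Bland-Altman mean difference. The change is worth making because slope and intercept are primary estimates and the correction is cheap.

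**What to change.** In Table 4 row 1.1 and section 8.2.1, report slope and intercept from an errors-in-variables fit: Deming regression, weighted for constant CV, with bootstrap or jackknife 95% confidence intervals.

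- **Reference error:** take it from the reference laboratory's control-result CVs. Section 11 already has the sponsor look at "availability of analyser calibration and control results", but only as an example of evidence, so the CVs must be requested.
- **POC error:** take the variance of this study's own differences, already planned in section 8.2.1, minus the reference-error variance. Do not use the CVs in Table 2. They are manufacturer claims that section 8.4 expects may be exceeded, and its definition of precision would already include reference error. Proportional bias adds little to this variance: with slope 0.95 and spread 11% it adds 0.05² × 121 = 0.3, against 20 for CVs of 2% and 4%.
- **Sensitivity:** show results over a range of reference CVs, because control CVs omit specimen differences.
- **Endpoint 1.2:** state which axis the proportional bias uses.
- **Keep** the ordinary regression line and R^2 as descriptive.

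The cost is a wording change and a few lines of R, with no extra samples. The small downside is that a reference CV must be obtained and stated.

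### Proportional bias in primary endpoint 1.2 is taken from the trend of the Bland-Altman difference, and measurement error alone can produce that trend on either concentration axis

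*Protocol*

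**What the plan says.** Protocol Table 4, row 1.2, gives the analysis of the second primary endpoint: "Point estimates of fixed and proportional bias (with 95% confidence interval), coefficient of variation and limits of agreement, calculated via Bland-Altman analysis". This applies to every marker and device, on both the absolute and the relative scale. The text of section 8.2.1 then explains the term: "proportional bias (dependence of the difference on concentration level), with 95% confidence intervals, will be computed". So the estimator is a trend of the POC-minus-reference difference over concentration. The protocol does not say whether concentration means the average of the two methods or the reference value, and it does not mention error in either method.

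The planning values are in section 8.4: "the Pearson's correlation coefficient and precision were conservatively assumed to be 0.9 and 5%, respectively". The same section explains the 5%: "The precision estimated as the standard deviation of difference of measurements compared to reference divided by the mean concentration (%CV"). It therefore combines POC and reference error. The protocol gives no precision figure for the reference assay, so the split is unknown.

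**The concern.** A difference between two noisy measurements is correlated with each of them, and usually with their average, even when the device has no bias. On the mean axis, a POC device that is only noisier than the laboratory appears to over-read progressively at high concentrations. On the reference axis, error in the reference makes the same device appear to under-read there. Either way, part of what is reported as proportional bias, with a confidence interval, is imprecision.

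The two primary endpoints could also point in opposite directions. If the regression in endpoint 1.1 is ordinary least squares of POC on reference (the protocol does not state the direction), its slope minus 1 is the reference-axis figure. With a reference SD of 2%, an unbiased device would then be expected to show -3.5% under 1.1 and, on the mean axis, +7.3% under 1.2.

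**Working it through.** **Inputs.** From Protocol section 8.4: ρ = 0.9, SD of difference 5% of the mean, n = 400. Assumed, because the protocol does not give it: reference error SD b½ = 1%, 2% or 3% of the mean, with the extremes 0 (error-free reference) and 3.54% (equal errors, √12.5). The model has no bias: P = T + e_P and R = T + e_R, with independent errors of constant SD and a mean concentration of 100.

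**The plan's own figures.** There is none for proportional bias. The interval for ρ reproduces: atanh(0.9) ± 1.96/√397 = 1.472 ± 0.098, giving 0.880 to 0.917. The minimum of 337 samples does not follow from a 5% SD of difference and a 1.5% bias: a paired t-test needs 90, and 337 needs an SD of 9.8%. That is a separate matter, but 9.8% is tried below as an alternative reading.

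**Step 1: between-person variance V.** Let a and b be the POC and reference error variances, with a + b = 25. From ρ = V/√((V+a)(V+b)) = 0.9,

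0.19V² − 20.25V − 0.81ab = 0.

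**Step 2: slope of the difference on the mean.** Covariance (a − b)/2 over variance V + (a + b)/4.

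**Step 3: slope of the difference on the reference.** −b/(V + b).

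| Reference SD | a, b | V | Mean axis | Reference axis |
|---|---|---|---|---|
| 0% | 25, 0 | 106.6 | 12.5/112.8 = +11.1% | 0 |
| 1% | 24, 1 | 107.5 | 11.5/113.8 = +10.1% | −1/108.5 = −0.9% |
| 2% | 21, 4 | 109.8 | 8.5/116.1 = +7.3% | −4/113.8 = −3.5% |
| 3% | 16, 9 | 112.1 | 3.5/118.3 = +3.0% | −9/121.1 = −7.4% |
| 3.54% | 12.5, 12.5 | 112.5 | 0 | −12.5/125 = −10.0% |

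The two artefacts are equal in size when b = 6.25, a reference SD of 2.5%: both are 5.3%, with opposite signs. If the reference were the noisier method, the mean-axis slope would also be negative.

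**Step 4: simulation.** With n = 400 and 3,000 unbiased studies per case, mean-axis slopes averaged +10.0%, +7.3% and +3.0% for reference SD 1%, 2% and 3% (standard error about 2.3 points). The 95% interval excluded zero in 99%, 88% and 25% of studies. On the reference axis it did so in 8%, 32% and 91%. A Deming slope with the correct error-variance ratio averaged within 0.1 percentage point of no bias in every case.

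**Step 5: sensitivity.** Mean-axis slope for reference SD 1%, 2%, 3%:

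- ρ = 0.95: +4.8%, +3.5%, +1.4%.
- ρ = 0.98: +1.9%, +1.4%, +0.6%.
- ρ = 0.99: +0.9%, +0.7%, +0.3%.
- ρ = 0.9, with 5% read as the POC's own SD: +10.1%, +7.8%, +5.0%.
- ρ = 0.9, with an SD of difference of 9.8%: +10.8%, +10.1%, +8.8%.

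**Scale.** At reference SD 2%, the between-person SD is √109.8 = 10.5% of the mean. Two such SDs above the mean, the false slope implies 0.073 × 21 = 1.5% apparent over-reading. That is as large as the fixed bias the study is sized to detect.

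**The case against.** The strongest reply is that the protocol leaves the x-variable open and defers detail to a SAP that is not at hand, so no wrong axis has been chosen. The first half is right. A reader might infer that the plan commits itself to the mean axis, or that ρ = 0.9 and a 5% SD by themselves give a false slope of +3% to +10%. The documents support neither: the axis is not named, and the range needs a reference SD that the protocol does not state. But leaving the axis to the SAP does not cure the problem. What the protocol does fix, a trend of the difference, is biased on both axes except in special cases.

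Second, ρ = 0.9 is a deliberately cautious value. With a 5% SD it implies a between-person SD of only about 10.5% of the mean, while Table 5 claims correlations of 0.981 to 0.998. If the between-person SD were 20%, 30% or 40% (also assumptions), the mean-axis slope at reference SD 2% would be 8.5/406.25 = +2.1%, 8.5/906.25 = +0.9% or 8.5/1606.25 = +0.5%. This stands: the larger figures belong to the cautious case. Even so, section 8.4 chose that case because field performance may be worse than claimed.

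Third, no acceptance limit is attached to proportional bias, and it is reported beside several other estimates and plots. This also stands and limits the consequence.

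A reader might also think that naming the reference value as the axis is enough. It is not. Above a reference SD of 2.5%, at the planning values, it gives the larger artefact. It would also only restate the endpoint 1.1 slope minus 1, if that regression is POC on reference.

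**Conclusion.** The point holds in conditional form. The protocol's definition of proportional bias does not separate a true concentration-dependent bias from measurement error. The expected error is zero on the mean axis only with equal error variances, and zero on the reference axis only with an error-free reference. At ρ = 0.9 and a 5% SD of difference, with a reference no noisier than the POC device, it lies between 0 and about +11% on the mean axis and between 0 and about −10% on the reference axis. At the correlations above 0.98 cited in section 8.4, the mean-axis artefact is below about 2%.

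These figures rest on an assumed reference SD, independent errors of constant SD, and slopes in absolute units. They do not show that the study's conclusions would be wrong. They show that one primary estimate can mislead under the plan's own cautious assumptions and is cheap to improve.

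**What to change.** In Table 4, row 1.2, and in the text of section 8.2.1, define proportional bias as the slope minus 1 from a Deming regression of POC on reference, with a 95% confidence interval. Use the weighted form if errors scale with concentration. State the error-variance ratio for each marker and device: take the reference error variance from the laboratory's quality-control records, and the POC error variance as the squared SD of the difference minus that. Report the result over a range of ratios, because this subtraction assigns to the POC device everything that is not analytical error in the reference, including capillary-venous differences and any true proportional bias. Keep Bland-Altman for fixed bias, limits of agreement and the plots.

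The cost is a sentence or two and a few lines of R. The laboratory's quality-control CV must be obtained for each marker; sections 6.3.2 and 11 indicate that control results are produced and looked at before the study starts. The downside is that the estimate depends on the assumed ratio, which is why the sensitivity range belongs in the report.
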